### **5.1.3 Alignment with intended study population**

The study population includes patients likely to benefit from using LLLT to make a difference in providing better analgesia.

### **5.1.4 Alignment with intended use of the device**

The study involves using the Er,Cr=YSGG Laser to perform cavity preparation without giving any injection anesthesia. On each patient subject that has two similar size cavities of the same classification, either Class I or Class V, on similar teeth. Two different laser protocols will be used. One includes Low Level Laser Therapy (LLLT) to condition the pulp producing analgesia before using higher power to perform the cavity prep. The other protocol will skip the LLLT setting and prepare the cavity with the higher power to perform the cavity prep.

## **5.2 Recruitment Methods**

### **5.2.1 Recruitment for Laser Analgesia Study**

Eligible patients will be invited to participate in the study, subject to [name] recruitment goals. They will be informed of the possible risks of the procedure and will be required to give informed consent before study-specific procedures can proceed. Each subject will be informed that no personally relevant clinical information will be derived from the collected data.

### **5.2.2 Duration of study activities**

This study is anticipated to continue until the desired number of patients have had the study completed on them. In the event that additional studies are going to be conducted, new protocols will be developed specifically for those studies.

## **5.3 Patient Selection**

The eligibility criteria for prospective enrollment of subjects are shown in **Table 1**.

**Table 1. Inclusion/Exclusion Criteria for Enrollment of Subjects**

Inclusion criteria	The study population will be representative patients that include adults 19-65 years old who had at least two cavity preparations of the same type, with the same approximate size lesion. Small & Medium size cavities
Exclusion criteria	Excluded patients include children, pregnant women, immune compromised patients, patients with heart disease, uncontrolled hypertension, cardiac arrhythmia, patients whose teeth amalgam restorations were in close proximity to the lesion, decay that has reached the pulp where potential for root canal therapy, patients of different language difficulty, and special/ vulnerable patient populations will be excluded.
Participant Withdrawal Criteria	Your participation in this study is voluntary. It is up to you to decide whether or not to take part in this study. If you decide to take part in this study, you will be asked to sign a consent form. After you sign the consent form, you are still free to withdraw at any time and without giving a reason. Withdrawing from this study will not affect the relationship you have, if any, with the researcher. If you withdraw from the study before data collection is completed, your data will be returned to you or destroyed.

## **6 STUDY MATERIALS**

### **6.1 Investigational Product**

#### **6.1.1 Identity of the investigational product and accessories**

- Waterlase MD (mfg: Biolase Technology Inc, Irvine CA)
- Waterlase MD accessories and consumables ( MG6 fiber tips, trunk fiber, contra-angle hand piece)
- Case Report Forms

#### **6.1.2 Safety issues**

If patient complains of having pain, raising hand signal, injection anesthesia will be given as an option to finish the procedure but will not be included in the study.

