## SYNOPSIS

Title of Study	Clinical Study of Laser Analgesia in Cavity Preparations using the Er,Cr:YSGG Laser
Objectives	To show there is laser analgesia. Restorative dental procedures potentially can be performed without needle injection first.
Planned Number of Subjects and Duration of Involvement	The planned number will be forty-eight patients. The duration will last till all patients are done.
Patient Population	Patients included in the study are adults 19-65 years old who had at least two cavity preparations of the same type, with the same approximate size lesion. Excluded patients include children, people with language barriers, pregnant women, immune compromised patients compromised (No bronchitis, no sinus infection, no ear infection, ect...), patients with heart disease, uncontrolled hypertension, cardiac arrhythmia, and patients whose teeth amalgam restorations were in close proximity to the lesion.
Investigational Product Name	Clinical Study of Laser Analgesia in Cavity Preparations using the Er,Cr:YSGG Laser
Methodology Overview	The study involves using the Er,Cr:YSGG Laser to perform cavity preparation without giving any injection anesthesia. This study is going to be done to show there is laser analgesia.

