## 4 STUDY OVERVIEW

### 4.1 Study Approach

[figure not shown]
**Treatment.** Preconditioning and cavity preparation are done using the Er:Cr:YSGG laser, Waterlase MD (mfg: Biolase Technology Inc, Irvine CA), and the gold hand piece with an MG6 fiber tip, trunk fiber, contra-angle hand piece. *Preconditioning.* Preconditioning is preformed using laser desensitization. One tooth will be randomly selected, and preconditioning will be performed using LLLT on the tooth with minimal tooth ablation. The LLLT settings that will be used for preconditioning are 0.25 Watts, 50 Hz, 0% water, 0% air, H mode. Following this a fiber-optic tip will be aimed perpendicular to the surface of the cervical portion of the tooth, ensuring that a 2mm distance will be maintained between the end of the fiber optic tip and the surface. The fiber-tip will be used to generate a 2mm line. The cavity on the second tooth will be prepared for without laser preconditioning. *Lesion Preparation – small preparations.* Small preparations are to be performed as follows. The Waterlase MD is set to 4.5W, 15 Hz, 65% air, and 60% water and the cavity is prepared according to the preferred technique. If patients indicate sensitivity, the procedure will be halted, patients fill out the VAS form and anesthetic will be offered. For patients who refuse anesthetic, the procedure will be continued at the same settings. *Lesion Preparation – small to medium preparations.* Small to medium preparations will be performed as follows. The Waterlase MD will be set to 2W, 15 Hz, 65% air, and 60% water and the cavity will be prepared according to the preferred technique. If patients indicate sensitivity, the procedure will be halted, patients fill out the VAS form and anesthetic will be offered. For patients who refuse anesthetic, the procedure will be continued at the same settings.

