**Restoration.** *Overall VAS Score.* Up to 3 intra-operative VAS measurements are recorded. If a patient feels even the slightest amount of pain during the procedure, they will be instructed to raise their hand and the treatment will be paused. The patient is then asked to fill in the VAS form before the procedure will be continued. After conclusion of the cavity preparation, patients will be asked to mark one last VAS rating indicating the overall pain of the procedure. Patients that do not raise their hand throughout the entirety of the procedure will be given an overall VAS rating of zero. Data for each patient will be recorded and analyzed in this way.

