### **Explanation of VAS analysis**

The VAS scale will be presented to the patients using a standard explanation (zero, indicating no pain at all, to 100, representing the ‘worst pain patient had ever felt’). Patients will be asked to place a vertical line on the VAS scale to indicate his/her discomfort status. They are encouraged to stop the treatment if they encounter any pain. The number of hand raises, as defined by the protocol, will be recorded and analyzed (small and medium/large preparations are analyzed separately), represent the number of times during the procedure the patient felt sufficient discomfort to stop the procedure.

VAS data will be assessed by the following assumptions: The 'lower' the average score, the 'better' the mode of treatment. Once the patient marks their vertical line on the scale, a precise measurement, in millimeters, was taken from the “zero” line of the VAS scale to where the patient marked their line.

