#### **Preparation of Lesion:**

- A. Laser ablation- Small Preparation
  - a. Waterlase MD settings: 4.5W, 15Hz, 65% air, 60% water
  - b. Prepare cavity preparation using preferred technique
  - c. If the patient indicates sensitivity,
    - Halt the procedure
    - Have the patient mark the VAS form,
    - Offer anaesthetic; if refused, continue using the same settings
- B. Laser ablation- Small and Medium Preparation
  - a. Waterlase MD settings: 2W, 15Hz, 65% air, 60% water
  - b. Prepare cavity preparation using preferred technique
  - c. If the patient indicates sensitivity, either
    - Halt the procedure

- Have the patient mark the VAS form,
- Offer anaesthetic; if refused, continue using the same settings

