## **9.3 Planned Analyses**

The clinical study report will contain only information necessary to prove this phenomenon.

Statistical analysis will include the VAS forms from each procedure which will be used to show there is laser analgesia and potentially cavity preparations can be performed by using the laser without the need to give injection anesthesia first. The VAS form is used to show how much pain they are in and if any. All patient data will remain anonymous during analyses to maintain patient confidentiality.

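### Section 6.1.2 does not say what is left out of the study after a pain signal; if it is the tooth or the patient, the analysed set is selected on pain

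*Protocol*

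**What the plan says.** Section 6.1.2 deals with a patient who raises a hand in pain: "injection anesthesia will be given as an option to finish the procedure but will not be included in the study". This is the only sentence in the protocol on what happens, for the study, when anaesthetic is accepted.

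Section 4.1 sets out the procedure and the scoring. At a signal, "If patients indicate sensitivity, the procedure will be halted, patients fill out the VAS form and anesthetic will be offered". The workflow in Section 7.1 agrees and, like Section 4.1, goes on to cover refusal only: "Offer anaesthetic; if refused, continue using the same settings". On scoring, Section 4.1 states "Patients that do not raise their hand throughout the entirety of the procedure will be given an overall VAS rating of zero", followed by "Data for each patient will be recorded and analyzed in this way". Its explanation of the VAS analysis adds "The number of hand raises, as defined by the protocol, will be recorded and analyzed". None of these statements makes an exception for a preparation finished under injection.

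The aim in the Synopsis is that "Restorative dental procedures potentially can be performed without needle injection first". Section 9.3 repeats it as the use of the VAS forms: to show laser analgesia and that "potentially cavity preparations can be performed by using the laser without the need to give injection anesthesia first".

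**The concern.** The sentence in 6.1.2 is a rule about what belongs to the study, and only a pain signal brings it into play. If it takes out the tooth or the patient, inclusion in the analysis depends on the outcome being measured. The teeth lost would be those where laser preparation alone was not enough, which is the evidence most directly against the stated aim. No analysed tooth would have needed an injection, and that would be true by construction.

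The protocol would also disagree with itself, because Section 4.1 analyses each patient's data and the hand raises without exception. An analysis plan written later would inherit the conflict and might have to settle it after the scores were known.

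**Working it through.** **1. The passages side by side.** In 6.1.2 the grammatical subject of the exclusion is the injection. Taken literally, the injection is available but is not a study procedure. The sentence can also be read as leaving out the rest of the procedure, the tooth or the patient. Sections 4.1 and 7.1 continue those who refuse and do not mention the data of those who accept. Section 11.1 repeats that injection is an option and says nothing about data. No passage settles it.

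**2. Who could be removed.** Anaesthetic is offered only after a signal. A tooth without a hand raise scores 0 under Section 4.1 (Section 7.1 does not repeat this rule). So only a tooth with a hand raise can trigger removal. An automatic zero can be lost only as the partner of such a tooth.

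**3. Effect on mean VAS and hand raises, if injected teeth are dropped.** The protocol gives no injection rate and no VAS value, so the inputs are assumed. Let h be the share of teeth with a hand raise, a the share of those finished under injection, and m the mean score of hand-raise teeth, taken as the same for acceptors and refusers.

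- All started teeth: mean VAS = h·m; hand-raise share = h.
- After removal: mean VAS = h(1−a)m / (1−ha); hand-raise share = h(1−a) / (1−ha).
- Ratio in both cases: (1−a) / (1−ha). The mm scale cancels.

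| h | a = 0.25 | a = 0.50 | a = 0.75 |
|---|---|---|---|
| 0.2 | 0.789 | 0.556 | 0.294 |
| 0.4 | 0.833 | 0.625 | 0.357 |
| 0.6 | 0.882 | 0.714 | 0.455 |

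Over this grid the reported values are 29% to 88% of those over all started teeth. If injected teeth score higher than refusers' teeth, mean VAS falls further. At a = 1 the ratio is 0 whatever pain was felt. That is a limit, not a forecast, since Sections 4.1 and 7.1 provide for refusal.

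**4. Pairs.** The one protocol figure used is 48 patients with two teeth each (Sections 5.1.1 and 9.1). It reproduces with 1.96 in both places: 1.96²×50×0.25 / (0.025²×50 + 1.96²×0.25) = 48.02 / 0.99165 = 48.42. The 1.69 printed in the numerator would give 36.00, which does not bear on this point. There is no allowance for excluded teeth. Complete pairs left range from 48(1−ha)², if injections fall independently on the two teeth, to 48(1−ha), if they fall in the same patients:

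- h = 0.2, a = 0.25: 43.3 to 45.6
- h = 0.4, a = 0.50: 30.7 to 38.4
- h = 0.6, a = 0.75: 14.5 to 26.4

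**5. LLLT contrast.** Two sets of simulations were run on assumed values: paired normal scores clipped to 0–100, with the pair dropped if either tooth is injected.

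- *Acceptance at random among hand-raisers.* Latent mean 15 without LLLT, SD 25, correlation 0.5, LLLT benefit 10, half of hand-raisers injected: condition means fall from 19.25 and 12.67 to 12.64 and 7.45 mm, the difference from 6.58 to 5.19 mm, and 22.6 of 48 pairs remain. With correlation 0.3–0.7, benefit 5–15 and 25–50% injected, the difference shrinks by about 3% to 28%.
- *Acceptance driven by pain level.* Latent means 25 and 15, SD 20, correlation 0.5: the difference falls from 8.4 to 5.8 mm (all accept above 40 mm, 35 pairs), 7.4 mm (half accept above 40 mm, 41 pairs) or 4.35 mm (all accept above 30 mm, 25 pairs).

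These sets imply many hand raises: Φ(15/25) = 73% and Φ(5/25) = 58% of teeth in the first, Φ(25/20) = 89% and Φ(15/20) = 77% in the second. Most of this lies outside the 20–60% grid in step 3, so the figures should not be combined. The contrast could also move the other way. If mainly LLLT teeth were injected and dropped, the LLLT mean would fall more than the other mean and the difference would widen.

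**The case against.** The best case for the text is that it means only that the injection is not a study procedure. The grammar supports this. So does the placement: 6.1.2 sits under Study Materials, not with eligibility (5.3, Table 1) or analysis (9.3), where a data exclusion would be expected. Section 4.1 keeps each patient's data and collects a VAS at the halt when anaesthetic is offered. On this reading no tooth is lost. The argument has real weight, and it is why the point is conditional. It does not close the matter, because 6.1.2 alone speaks to the accepted case and could be followed as an exclusion. Even on this reading, the closing overall rating is marked after anaesthetic, and nothing says which score counts.

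A reader might go further and infer that the protocol excludes every patient who signals pain. The documents do not support that: Sections 4.1 and 7.1 carry on with those who refuse. A reader might also infer that exclusion would exaggerate the benefit of LLLT. The illustrations show attenuation, and the direction depends on who accepts.

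It can also be said that analysis sets belong in an analysis plan. That would answer a complaint about missing detail. Here the protocol itself states a rule that is unclear and, on one plausible reading, contradicts its own Section 4.1.

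**Conclusion.** The point holds in conditional form. Section 6.1.2 leaves open whether the injection, the tooth or the patient is outside the study. If teeth or patients are removed, the rule contradicts Section 4.1 and selects on pain. Mean VAS and hand raises are understated in favour of the no-injection claim, provided injected teeth score at least as high as those of patients who signal and refuse. Pairs are lost as well. The effect on the LLLT contrast is uncertain.

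The size is unknown. The 29–88% range, the pair counts and the simulated contrasts follow from assumed inputs and show direction and scale only. Confidence is medium, because the harmless reading is plausible. The text should still be fixed: the possible distortion is large and the correction cheap.

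**What to change.** Reconcile 6.1.2 with 4.1 and 7.1, for example:

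> Only the injection is outside the study. Every tooth on which any study laser step (LLLT preconditioning or preparation) was started stays in the analysis, except data withdrawn under Table 1. Acceptance of anaesthetic is recorded per tooth and reported by condition over all started teeth. For a tooth finished under injection, the VAS marked at the halt when anaesthetic was accepted is used, not the overall rating given afterwards. That mark is recorded even if three intra-operative marks already exist, and it is flagged as a halt score. A sensitivity analysis ranks these teeth worst.

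Naming preconditioning matters because a signal at that step can arise in the LLLT condition only. The provision on a further mark is needed because Sections 4.1 and 7.1 record at most three during the procedure.

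The cost is a few sentences, one extra item per tooth, an occasional fourth VAS mark and one sensitivity analysis. The drawbacks are that halt scores are mixed with overall ratings, hence the flag and the sensitivity analysis, and that results may look less favourable. When anaesthetic is offered does not change.

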## 3 STUDY OBJECTIVES

The principal objective of this study is to prove the phenomenon of laser analgesia. Traditionally before a cavity preparation is performed, the doctor will use local anesthetic (Needle Injection) before using rotary instrument to do a cavity preparation. The study involves using the Er,Cr=YSGG Laser to perform cavity preparation without giving any injection anesthesia. VAS (Visual Analog Scale) will be used to have patients rate the laser

cavity preparation procedure to show there is laser analgesia. On each patient subject that has two similar size cavities of the same classification, either Class I or Class V, on similar teeth. Two different laser protocols will be used. One includes Low Level Laser Therapy (LLLT) to condition the pulp producing analgesia before using higher power to perform the cavity prep. The other protocol will skip the LLLT setting and prepare the cavity with the higher power to perform the cavity prep. The design of the study is to find out if there is laser analgesia and if LLLT makes a difference in providing better analgesia. The VAS forms from each procedure will be used to show there is laser analgesia and potentially cavity preparations can be performed by using the laser without the need to give injection anesthesia first.

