**Restoration:**

- Overall VAS Score: Up to 3 intra-operative VAS measurements are recorded. If a patient feels even the slightest amount of pain during the procedure, they are instructed to raise their hand and the treatment would be paused. The patient will then be asked to fill in the VAS form. The procedure could then be continued. After the conclusion of the cavity preparation, the patients are asked to mark one last VAS rating indicating the overall pain of the procedure.

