# **11 RISK ANALYSIS**

## **11.1 Potential Risks of the Investigational Product and Clinical Investigation**

The procedures used in this study are experimental. However, there is no more of a risk during this study than there would be during any other cavity preparations performed by [name]. If you are having any pain during the procedure, we ask that you please signal us by raising your hand. We will stop the procedure and use injection anesthesia as an option to finish the procedure. You may decline to answer any or all questions and you may terminate your involvement at any time if you choose with no penalty.

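### Section 6.1.2 keeps something about rescue injection out of the study without saying what; dropping teeth or patients would select on pain, and keeping them leaves the overall VAS marked after anaesthesia

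*Protocol*

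**What the plan says.** Each patient has two similar cavities prepared by laser without prior injection, one after LLLT preconditioning and one without it. Section 7.1 (Workflow) places the LLLT tooth first.

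- **Rescue.** When a patient signals sensitivity, Section 4.1 has the procedure halted, then "patients fill out the VAS form and anesthetic will be offered". Section 7.1 gives the same order and ends with "Offer anaesthetic; if refused, continue using the same settings". Both describe what follows a refusal; neither says what happens to the data after an acceptance.
- **Exclusion.** Section 6.1.2 adds that "injection anesthesia will be given as an option to finish the procedure but will not be included in the study". Section 11.1 repeats the offer without a data rule: "We will stop the procedure and use injection anesthesia as an option to finish the procedure".
- **Outcomes.** Up to three VAS marks are taken during the procedure. After the preparation ends, "the patients are asked to mark one last VAS rating indicating the overall pain of the procedure". A patient who never raises a hand is scored zero overall. Hand raises are counted and analysed, and are said to "represent the number of times during the procedure the patient felt sufficient discomfort to stop the procedure".
- **Aim.** Section 3 states: "The VAS forms from each procedure will be used to show there is laser analgesia and potentially cavity preparations can be performed" by laser without an injection first. Section 9.3 repeats this.

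**The concern.** The protocol writes in an exclusion and leaves its scope open. This is more than detail deferred to an analysis plan, because the two main ways of following the sentence lead to different data and each has a cost.

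- **Tooth or patient left out.** Anaesthetic is offered only after a pain signal, so accepting it depends on the outcome. The painful end can leave while patients with no hand raise stay in at zero. The remaining set holds only preparations finished without injection, although accepting an injection is a direct failure of the aim in Sections 3 and 9.3.
- **Only the injection or the later data left out.** The overall VAS of a rescued tooth is then marked after anaesthesia, or is missing if later data are dropped. The raise count stops at rescue. Both understate pain on the teeth that hurt most.

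Either way the comparison of LLLT with no LLLT is disturbed. If the scope is settled only after scores are seen, the choice could also follow the result.

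**Working it through.** **The plan's own figure.** The protocol gives no rescue rate, VAS mean or SD. The only figure used here is its sample size. With c = 1.96, N = 50, p = 0.5 and A = 0.025, n = (1.96² × 50 × 0.25) / (0.025² × 50 + 1.96² × 0.25) = 48.02 / 0.99165 = 48.42, as stated. (The substitution line prints 1.69 in the numerator, which would give 36.0; the stated result follows from 1.96.)

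**Assumed inputs, for illustration only.** Peak VAS is normal with mean 45 mm without LLLT and 35 mm with it, SD 20, limited to 0–100, with correlation 0.5 between a patient's two teeth. Anaesthetic is accepted above a cut-off by all patients or by half of them. Results come from 2,000,000 simulated pairs. Full data give means 45.1 and 35.3, difference 9.75 mm.

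**Share rescued at 60 mm, all accepting.** Without LLLT: 1 − Φ((60 − 45)/20) = 1 − Φ(0.75) = 0.227. With LLLT: 1 − Φ((60 − 35)/20) = 1 − Φ(1.25) = 0.106.

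**Teeth or patients dropped, cut-off 60 mm**

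| Acceptance | Pairs left of 48 | Means (no LLLT, LLLT) if pairs dropped | Difference, pairs dropped | Difference, only teeth dropped |
|---|---|---|---|---|
| Nobody dropped | 48 | 45.1, 35.3 | 9.75 | 9.75 |
| All accept | 35 | 36.7, 29.1 | 7.6 | 6.1 |
| Half accept | 41 | 41.6, 32.7 | 8.8 | 8.3 |

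Over cut-offs of 50 to 70 mm and half to all accepting, 25 to 45 pairs remain. Dropping pairs lowers mean VAS by 1.5 to 13.7 mm. The difference is 6.5 to 9.2 mm (pairs dropped) or 4.6 to 8.7 mm (teeth dropped). With no LLLT effect (both means 45) the difference stays at 0, but at 60 mm mean VAS still falls from 45.1 to 35.9 (all accept) or 41.4 (half).

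A lower pain level gives the same direction. With means 20 and 10 before limiting to 0–100, and cut-off 40 mm, full data give 21.7 and 14.0 (difference 7.7). Dropping teeth gives 16.2 and 11.5 (4.8 after rounding the unrounded means). Dropping pairs gives 15.8 and 10.2 (5.6), with 81% of patients kept.

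**Teeth kept, overall VAS marked after anaesthesia.** If a rescued tooth is marked d mm lower, the difference is 9.75 − d × (0.227 − 0.106) = 9.75 − 0.121d. For d = 10, 20, 30 mm this is 8.5, 7.3 and 6.1 mm. With half accepting it is 9.1, 8.5 and 7.9 mm.

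**Numbing carried to the second tooth.** Worst case: an injection for the LLLT tooth, treated first, sets the second tooth's VAS to 0. The difference then falls by (share of LLLT teeth rescued) × (mean VAS the second tooth would have had).

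- Cut-off 50 mm, means 45 and 35, all accept. The share is 1 − Φ(0.75) = 0.227. The LLLT tooth averages 35 + 20 × 0.301/0.227 ≈ 61.6 in these patients, so the second tooth would average 45 + 0.5 × 26.6 ≈ 58.3. The loss is 0.227 × 58.3 ≈ 13.2, and the simulated difference is about −3.4 mm.
- Cut-off 60 mm, both means 45 (no true effect), all accept. The share and the loss are the same, so the difference is about −13 mm.
- Cut-off 60 mm, means 45 and 35, all accept. The share is 0.106, the second tooth would average 45 + 0.5 × 20 × 0.183/0.106 ≈ 62.3, and the loss is about 6.6. The difference is about 3.2 mm: smaller, not reversed.

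**The case against.** The strongest reply is grammatical. The only subject of the clause in Section 6.1.2 is the injection, and it stands under safety, not under patient selection or analysis. Neither Table 1 nor Section 9.3 excludes rescued patients. This stands as far as it goes: a reader might infer that the protocol orders rescued patients to be dropped, and it does not say so. But it does not say that they stay either.

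A reader might also see a contradiction with Section 4.1, which says "Data for each patient will be recorded and analyzed in this way". That sentence closes a paragraph on how VAS is collected and how patients with no hand raise are scored. It describes scoring and does not define who is analysed, so it is no clear conflict.

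A cut-short raise count and an overall VAS marked after rescue follow from offering anaesthetic at all, which is ethically required. That is true. The halt, VAS, offer order also already secures a mark before any injection on that tooth. What is missing is a rule that such marks are kept and used.

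Finally, how rescue data are summarised may be left to an analysis plan. That is fair for the choice of VAS summary. It is not an answer for an exclusion that the protocol itself states.

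**Conclusion.** The point holds as an unclear rule that should be settled before pain scores are seen. Dropping rescued teeth or patients would lower mean VAS and leave only preparations finished without injection, which favours the trial's claim by construction. Keeping them without a further rule leaves the overall VAS and the raise count understating pain on rescued teeth.

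The size is unknown. Every input to the illustration except the 48 patients is assumed, and acceptors need not be exactly the highest scorers, although the trigger is pain.

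A reader might infer that the LLLT contrast can only shrink. The documents do not support that. Dropping cases shrank it in the scenarios with a true effect, but the LLLT tooth is treated first, and an injection there might numb the second tooth and even reverse the sign. Nor is reversal a prediction: it needs one injection to act on both teeth, and the protocol states neither that nor the time between the two preparations.

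**What to change.** 1. Amend Section 6.1.2 to say that a patient who accepts injection finishes the procedure under it, and that the patient and both teeth stay in the analysis.
2. Record on the case report form, per tooth, whether anaesthetic was accepted and at which hand raise.
3. For rescued teeth, compare pain using VAS marked before anaesthetic, which Sections 4.1 and 7.1 already collect, with the same kind of mark on the patient's other tooth. Report per tooth whether the preparation was completed without injection.
4. Flag a second tooth prepared while an injection for the first may still act. Where practical, do that preparation at a later time or visit. Otherwise repeat the LLLT comparison without such pairs as a sensitivity analysis.

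Item 1 belongs in the protocol; the analysis parts of items 3 and 4 could sit in Sections 4.1 and 9.3 or in an analysis plan.

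**Cost.** A few sentences, a few fields on the form, no extra patients, and a later visit for some rescued patients. The raise count becomes descriptive. The mark made before anaesthetic misses pain that would have come later, so it should be read together with completion without injection.
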